14.2 Analysis items and methods

Primary endpoint: change in SMI measured by BIA.

Change in SMI defined as SMI at week 12 - SMI at baseline, where SMI is calculated as limb muscle mass (kg) / height² (m²).

Each endpoint is a continuous quantity, and is based on data from a single time point.

The results of the analysis will be presented as the adjusted least square means ± standard error.

Subgroup analysis is performed with age and BMI as subgroups.

The incidence rate and 95% confidence interval will be presented for each adverse event.

1) Within-group comparison

Depending on the variability of the population, the corresponding *t*-test (paired *t*-test) or Wilcoxon signed-rank test will be used to compare the measurements before, 6 weeks after, and 12 weeks after intake. In cases where the aforementioned analysis methods do not apply, a statistical method more appropriate for aggregated data will be employed.

2) Between-group comparison

Depending on the variability of the population, the unpaired *t*-test or Mann–Whitney U test will be used to compare the measured values before, 6 weeks after intake, and 12 weeks after intake, and calculate the corresponding changes. The difference between pre-and post-intake values will be compared between groups. Analysis of covariance will be performed if the pre-intake values cannot be ignored as confounding. In addition, treatment comparison is performed using mixed model analysis. When endpoints cannot be calculated using mixed model analysis, endpoints follow mixed-effect model for repeated measures (MMRM). In other cases where the aforementioned analysis methods do not apply, a statistical method more appropriate for aggregated data will be employed.

3) Safety evaluation

Analysis will confirm the absence of any changes associated with the intake of test foods that would require medical attention.

4) Standards and software

Statistical analysis shall be conducted using a two-tailed test, and the significance level shall be set at 5%. Participants who do not comply with the study requirements, such as an intake rate of less than 90%, will be excluded from the analysis.

Secondary endpoints: changes to physiological markers of aging determined by (1) physical measurements, (2) blood tests, (3) physiological tests, (4) radiological examination, (5) questionnaires, and (6) diary (see 7 “Evaluation items”) will be assessed in the same way as the main evaluation items above. The correlation between blood levels of NAD-related metabolites (NAD, nicotinamide, NA, NR, NAR, NAMN, NAAD, tryptophan, methyl nicotinamide, quinolinic acid, glutathione, AMP, ADP, and ATP) before oral administration and measured aging markers will be calculated using Pearson's product rate correlation coefficient (normal distribution) or Spearman's rank correlation coefficient (non-normal distribution). The effect of various endpoints on the different parameters will be analyzed. In cases where the aforementioned analysis methods are not applicable, statistical methods more appropriate for aggregated data will be employed.

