6.11 Actions taken after completion of the study

After completion of the study, research participants will return to their habitual dietary habits and no special measures will be taken.

6.12 Preservation of samples obtained from human participants and information used in the research

1) Anonymization of samples and storage method

After samples are obtained, they will be promptly anonymized by deleting any personal identifiers, such as names and registration IDs; instead, a research identification number will be attached. The anonymized samples will be measured immediately or stored at the P1 Unit, University of Tokyo Hospital, where access privileges are restricted by a locked door, at -80°C until the end of the study. After the measurement is completed or the storage period has elapsed, the identification number will be deleted by cutting the identification label, and the samples will be disposed of.

2) Anonymization of information and storage method

After the information is obtained, it will be anonymized by immediately deleting any personal identifiers, such as names and medical record IDs, and will be replaced by a research identification number. A correspondence table that can be linked to personal information will be created. The anonymized information and the correspondence table will be held in the laboratory of the person in charge of management (A501 and 618, Clinical Research Building, University of Tokyo Hospital) in separate storage rooms with locked and restricted access.

3) Storage period and disposal method

Information related to this research will be stored for 5 years from completion of the study or three years from the final publication of the study results, whichever is later, and then disposed of in an unrecoverable form by shredding the printed media or deleting the electronic files.

7. Evaluation items

Primary endpoint: change in SMI measured by bioelectrical impedance analysis (BIA).

Secondary endpoints: changes in markers of physiological aging determined by: (1) physical measurements, (2) blood tests, (3) physiological tests, (4) radiological examination, (5) questionnaires, and (6) diary.

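### Section 14.2(2) tests the arms on raw values before and after intake as well as on the change, which gives each endpoint a second, baseline-dependent efficacy test that is not the defined endpoint

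*Protocol*

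**What the plan says.** Section 7 names the change in SMI as primary and changes in markers of aging as secondary. Section 14.2 fixes the primary as "Change in SMI defined as SMI at week 12 - SMI at baseline".

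Under Between-group comparison, section 14.2(2) uses the unpaired t-test or Mann–Whitney U test to "compare the measured values before, 6 weeks after intake, and 12 weeks after intake, and calculate the corresponding changes". A separate sentence adds: "The difference between pre-and post-intake values will be compared between groups". Baseline adjustment is conditional: "Analysis of covariance will be performed if the pre-intake values cannot be ignored as confounding". A mixed model comparison is planned in addition, with MMRM as the fallback. The two-tailed 5% level is set for the statistical analysis as a whole, and no comparison is labelled descriptive.

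The secondary endpoints, also defined as changes, "will be assessed in the same way as the main evaluation items above", so the double testing reaches all of them.

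Section 6.10 asks that age, SMI and BMI should not differ significantly between groups at allocation. The schedule in section 8 places body measurements at screening and week 12 only, so SMI has no week-6 value. The week-6 comparisons concern other endpoints, such as FMD.

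**The concern.** Two different quantities are tested for one effect. The pre-intake comparison is made before anyone has taken the test food, so a significant result there carries no information on NMN. The raw week-12 difference equals the baseline gap plus the difference in change, so it mixes chance imbalance with the effect of interest and is not the endpoint that the protocol defines.

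Two things are at stake. With no effect, each endpoint gets a second chance of a significant result. With a real effect, the report can show a significant change beside a non-significant raw comparison, or the reverse. Another sentence in 14.2, "Each endpoint is a continuous quantity, and is based on data from a single time point", fits poorly with a change from baseline and does not help a reader decide which quantity is meant.

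**Working it through.** **Inputs.** From section 14.1: SD of SMI 0.60 kg/m², expected difference 0.45 kg/m², 21 enrolled per arm. From 14.2: two-sided 5%. Assumed, because the protocol does not give it: correlation r between baseline and week 12, from 0.5 to 0.95, with equal SDs at both visits. The lower end is the value at which the SD of the change is itself 0.60.

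**The plan's own figure.** The protocol states no power and no error rate for these comparisons. Its 20 per group is not reproduced at an assumed 80% power: 2 × (1.960 + 0.842)² × 0.60² / 0.45² = 27.9, so 28 per group. At 20 per group the two-sided power is 64% (t distribution). That is a separate matter, and nothing below depends on it.

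**Step 1: the baseline gap.** Its standard error is 0.60 × √(2/21) = 0.185 kg/m². The largest non-significant gap is 2.021 × 0.185 = 0.374 kg/m², which is 83% of 0.45. The balance rule in 6.10 therefore limits the SMI gap but does not remove it.

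**Step 2: how the gap carries over.** Given a gap g and no effect, the expected raw week-12 difference is r × g and the expected difference in change is −(1 − r) × g. At r = 0.5 each carries half, in opposite directions. At r = 0.95 the raw test carries almost all of it. An analysis with baseline as covariate carries none in expectation.

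**Step 3: relation of the two tests.** The SD of the change is 0.60 × √(2(1 − r)). The correlation between the raw week-12 contrast and the change contrast is √((1 − r)/2). Two independent 5% tests would give 1 − 0.95² = 9.75%.

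**Step 4: results.** From simulation with t-tests, 21 per arm, 200,000 trials per row. Balanced means that the baseline SMI gap is non-significant.

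| r | SD of change | Correlation of contrasts | Either significant, no effect | Same, balanced | Raw power at 0.45 | Change power at 0.45 | Tests disagree at 0.45 |
|---|---|---|---|---|---|---|---|
| 0.5 | 0.600 | 0.50 | 9.3% | 7.8% | 66% | 66% | 31% |
| 0.7 | 0.465 | 0.39 | 9.4% | 7.5% | 66% | 87% | 32% |
| 0.8 | 0.379 | 0.32 | 9.6% | 7.3% | 66% | 96% | 33% |
| 0.9 | 0.268 | 0.22 | 9.6% | 6.7% | 66% | over 99.9% | 34% |
| 0.95 | 0.190 | 0.16 | 9.7% | 6.2% | 66% | over 99.9% | 34% |

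Without the balance condition the raw test alone is significant in about 5% of no-effect trials at every r. With it, the raw SMI test alone falls to between 4.4% (r = 0.5) and 1.6% (r = 0.95). The disagreement rate with balanced baselines is 29–33%.

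**The case against.** Several points on the other side stand.

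- A reader might infer that the raw week-12 test is biased or has an inflated error rate. It does not: over randomization it holds 5%. A baseline gap that shows up as a week-12 difference is part of that ordinary 5%. The problem is the extra test, not bias in expectation.
- A reader might apply the 9–10% figure to the primary endpoint. Section 6.10 restricts the SMI gap, and 6–8% is the fair range there if the rule is met. The higher figure belongs to endpoints with no balance rule.
- One can condition on a gap of 0.37, at the edge of what the rule allows, and find the raw test falsely favouring the higher arm in 24–35% of trials (r = 0.8–0.95). That is a corner case, not the expected behaviour.
- The raw test is not always the weaker one. At r = 0.5 the powers are equal. A high r is plausible for SMI but not established for questionnaires, IL6 or metabolites.
- It would be too strong to say that nothing tells the reader which p-value counts. Sections 7 and 14.2 both name the change as primary, and ranking supportive tests is commonly left to an analysis plan.
- The pre-intake comparison has a use within the protocol's own scheme, since 6.10 sets a non-significance criterion and 14.2 makes ANCOVA depend on pre-intake values. It still gives no evidence on NMN.

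What does not fall away is that the protocol itself prescribes the raw between-arm tests. This is a stated rule, not detail left for later. The adjusted least square means mentioned in 14.2 and the additional mixed model do not cancel those tests.

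**Conclusion.** The point holds as an avoidable analysis choice of modest severity. Section 14.2(2) adds raw-value tests to endpoints defined as changes. Under normal data with SD 0.60, 21 per arm and r = 0.5–0.95, this raises the chance of at least one significant result under no effect from 5% to about 9–10% per endpoint where baseline is not balanced, and to about 6–8% for SMI where the 6.10 rule is met. At a true 0.45 kg/m² difference the raw test has about 66% power, against 66% to over 99.9% for the change. All these figures depend on the assumed r.

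The documents do not support saying that the primary result is corrupted: the change is tested regardless, it is the named primary endpoint, and the study calls itself exploratory.

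**What to change.** In 14.2(2), delete the between-arm tests of measured values before, 6 weeks after and 12 weeks after intake. Show those values by arm and visit descriptively, and give no p-values for pre-intake differences.

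Name one baseline-adjusted analysis of the change as the between-arm efficacy test for each endpoint. This would be ANCOVA with the pre-intake value as covariate in all cases, no longer conditional. Where week 6 is measured, it could instead be the planned mixed model or MMRM with the pre-intake value as covariate. Label any model that remains as supportive, so that the mixed model does not become an unranked second efficacy test.

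The cost is a rewording and a decision on the role of the mixed model. No new data are needed and fewer tests are run. Readers lose p-values on raw levels but still see the values by arm.

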3.2 Anticipated adverse reactions due to participation in the study

Allergic symptoms, gastrointestinal symptoms (e.g., diarrhea), facial flushing, liver damage.

4. Eligibility

Healthy elderly people who meet the following criteria (recruitment is entrusted to Newing NPO Corporation, Tokyo, Japan) are eligible for the study.

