7.6 Daily diary

During the intake period, the presence/absence of test food intake, physical condition, and dietary survey will be recorded daily in a designated diary.

8. Observation and test items, methods of data collection

Schedule				
items	Screening	Baseline	Supplement period	
Period	1-4weeks before	Week 0	Week 6	Week 12
Visit	1	2	3	4
Obtaining consent	○			
Background	○			
Supplement intake		←—————→		
Subjective symptoms	○	○	●	●
Confirmation of adverse events	←—————→			
Vital signs	○			●
Body measurements	○			●
Blood test 1	○			●
Blood test 2		○		●
75g OGTT		○		●
FMD test		○	●	●
Bone density test		○		●
Radiological examination		○		●
Questionnaires		○	●	●
Diary		←—————→		

Items marked with ○ are to be assessed before the start of supplements intake.

Items marked with ● are to be assessed after the start of supplements intake.

- 1) Background: gender, date of birth, height, weight, and medical history.
- 2) Supplements intake: record of start and end dates.
- 3) Subjective symptoms and other findings: to be confirmed by interview or other means.
- 4) Confirmation of adverse events and side effects: adverse events include various laboratory abnormalities.

The nature, timing of onset and disappearance, degree, treatment, outcome, evaluation of severity, and relationship to the study drug should be described in the medical record and case report. Follow-up studies should be conducted if necessary. The severity of the disease will be defined as 1) mild: the patient can continue the trial without treatment, 2) moderate: the patient can continue the trial with some treatment, and 3) severe: the patient should stop or discontinue the trial. Serious adverse events are defined on a scale of 10 and should be reported promptly if applicable.

5) Vital signs: blood pressure, pulse rate, respiratory rate, body temperature, and oxygen saturation.

6) Body measurements: height, weight, body composition (BIA method), waist circumference, leg circumference, grip strength, visual test, hearing test, 30-s chair stand test, and gait speed.

*Height is measured only during pre-intake screening.

7) Blood test 1: CK, total protein, albumin, uric acid, blood urea nitrogen (BUN), creatinine, sodium, potassium, as well as immunobiological tests for HBs antigen, HCV antibody, HIV antibody, and syphilis (STS and TPHA).

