8) Blood test 2: CRP, hormone tests (free testosterone, testosterone, DHEA-S, osteocalcin, pentosidine, and adiponectin), IL6, NAD metabolism-related metabolites (NAD, NMN, nicotinamide, NA, NR, NAR, NAMN, NAAD tryptophan, methyl nicotinamide, quinolinic acid, glutathione, AMP, ADP, and ATP). About 5 mL of whole blood is sent frozen to the Department of Metabolism and Nutrition, Graduate School of Medicine and Pharmaceutical Science for Research, Toyama University, for measurement using a mass spectrometer. After measurements, the sample will be destroyed and the data will be sent to the principal investigator.

9) 75g OGTT at 0 min, 30 min, 60 min, and 120 min; measuring blood glucose, insulin, serum-CPR.

10) FMD test.

11) Bone density test: performed using a bone densitometer.

12) Radiological examination: abdominal CT scan.

13) Questionnaire: common questionnaires about food attitude and anti-aging QOL, MMSE-J, and MoCA-J. *MMSE-J and MoCA-J are administered only at week 0 and week 12.

14) Diary: during the intake period, the participants' physical condition and dietary survey will be recorded daily in a designated diary.

On each visit, the patient will be asked to come to the hospital with a fasting breakfast and no test food intake to perform the test properly.

9. Discontinuation criteria

The following criteria will be considered grounds for discontinuing the research.

- 1) If the research participant declines to participate in the research or withdraws consent.
- 2) If the eligibility of the participant is found to be no longer valid after enrollment.
- 3) If it is difficult to continue the research due to adverse events.
- 4) If the entire study is discontinued.
- 5) If the physician deems it appropriate to discontinue the research for any other reason.

If the principal investigator and sub-investigators determine that it is impossible to continue the study for any reason, the date, reason, and course of discontinuation/withdrawal will be clearly stated in the medical record and case report, and necessary tests will be conducted at the time of discontinuation/withdrawal to evaluate efficacy and safety.

In the case of discontinuation due to an adverse event, treatment or follow-up observation should be conducted until the patient recovers as much as possible to the original state.

10. Handling in the case of an adverse event

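### The protocol's only rule on who is analysed excludes participants by intake after randomisation, so the primary SMI comparison is not as randomised, and the rule does not exempt safety.

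*Protocol*

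**What the plan says.** Section 14.2, item 4 (Standards and software) gives the two-sided 5% test and then the rule: "Participants who do not comply with the study requirements, such as an intake rate of less than 90%, will be excluded from the analysis". It names no other analysis set and makes no exception for any endpoint.

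Other places that bear on it:

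- Section 7.6, on how intake is recorded: "During the intake period, the presence/absence of test food intake, physical condition, and dietary survey will be recorded daily in a designated diary".
- Section 3.2, on anticipated reactions: "Allergic symptoms, gastrointestinal symptoms (e.g., diarrhea), facial flushing, liver damage".
- Section 8, item 4, on the top severity grade for adverse events: "severe: the patient should stop or discontinue the trial".
- Section 9, among the grounds for discontinuation: "If it is difficult to continue the research due to adverse events". For those who stop, "necessary tests will be conducted at the time of discontinuation/withdrawal to evaluate efficacy and safety".
- Section 14.2, on adverse events: "The incidence rate and 95% confidence interval will be presented for each adverse event". Item 3 of the same section adds: "Analysis will confirm the absence of any changes associated with the intake of test foods that would require medical attention".
- Section 14.2 defines the primary endpoint as SMI at week 12 minus SMI at baseline. The schedule in Section 8 marks body measurements at screening and week 12 only.

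**The concern.** Randomisation makes the two arms comparable at the start. A rule that removes people for something that happens later keeps that comparability only if removal is unrelated to treatment and to outcome. Intake is such a later event. Diarrhoea, flushing or illness can lower it, and the people affected may also differ in how their muscle mass changes. What remains is a comparison of selected compliers, and the two-sided 5% test no longer has the guarantee that randomisation gives it.

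Two features of the wording add to this. Low intake is given only as an example of non-compliance, and the other study requirements that would lead to exclusion are not listed. The exclusion is also from the analysis as a whole. Since the top severity grade is defined by stopping, a literal application would tend to remove the most severe events from the incidence figures.

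This is not a detail left to a statistical analysis plan. A later plan that analysed everyone randomised would contradict the protocol sentence, so the sentence itself has to change.

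**Working it through.** **Inputs from the protocol.** 12 weeks of intake (Section 6.4); 21 participants per arm, 5% predicted dropout, SD 0.60 kg/m² and target difference 0.45 kg/m² (Section 14.1); 90% intake threshold (Section 14.2). The protocol gives no expected rate of non-compliance, so every count of excluded participants below is an assumption.

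**What the threshold means.** 12 × 7 = 84 days, and 0.90 × 84 = 75.6. At least 76 days of intake are needed, so 84 − 76 = 8 missed days are allowed and the ninth leads to exclusion. If the denominator is the planned 84 days, anyone who stops before about day 76 is excluded. The protocol does not define the denominator. If it is days until stopping, some early stoppers stay in.

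**Room in the sample size.** 21 × 0.05 = 1.05, about one person per arm. Section 14.1 does not say whether dropout includes exclusions under this rule.

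**Efficacy, one-arm scenario.** Assume no treatment effect, 21 per arm, and a correlation r between adherence and change in SMI. Remove the k least adherent from one arm only. The mean of those left shifts by

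bias (in SD) = r × S_k / (21 − k),

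where S_k is the sum of the expected absolute values of the k lowest of 21 standard normal values. The four lowest are about 1.888, 1.433, 1.160 and 0.953.

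- k = 2, r = 0.3: 0.3 × 3.321 / 19 = 0.052 SD.
- k = 4, r = 0.5: 0.5 × 5.434 / 17 = 0.160 SD.

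Simulation of 40,000 trials agrees: bias 0.05 to 0.16 SD, and type I error of about 5 to 8% for a nominal 5% t-test. At an SD of 0.60 kg/m² this is 0.03 to 0.10 kg/m², and 0.16 × 0.60 / 0.45 = 21% of the target difference at the upper end.

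**Efficacy, other scenarios.** Removing the same 2 to 4 from both arms gives a bias of essentially zero and a type I error of about 5 to 6%. Removing one person from one arm, in line with the 5% dropout, gives 0.03 to 0.05 SD and an error of about 5.2 to 5.5%.

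**Safety, assumed counts.** Suppose 2 of 21 in one arm stop early for an adverse event and both fall under the rule.

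| Set | Incidence | Exact 95% CI |
|---|---|---|
| As randomised | 2/21 = 9.5% | 1.2 to 30.4% |
| After exclusion | 0/19 = 0% | 0 to 17.6% |

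**The aim of confirming absence.** Even with nobody excluded, zero events among 21 leaves an exact two-sided upper limit of 1 − 0.025^(1/21) = 0.161. A true rate of 16% would not be ruled out.

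**The case against.** The strongest reply has five parts.

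*The safety loss is inferred.* A reader might conclude that the adverse-event tables will drop those who stop, and that the tests done at discontinuation are thrown away. The protocol does not say so. The rule sits beside the test settings, safety is a separate item, and adverse events are recorded for all participants, with follow-up of those who stop because of one. This stands. The supportable statement is that the wording makes no exception for safety and could be applied to it.

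*The bias figures come from a one-sided scenario.* This also stands. The number removed, the imbalance between arms and the correlation are all assumed. Section 6.9 lets a forgotten dose be taken later the same day, which limits missed days. The figures show what the rule permits and are no forecast.

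*Choosing exclusions with outcomes in view is speculation.* A reader might infer this from the open-ended list. Allocation is withheld until the end of the study (Sections 6.8 and 6.10), and the timing of such decisions is often left to an analysis plan. What remains is that the criteria are not closed.

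*Incidences with confidence intervals are already planned.* Correct. Only the between-arm difference would be new, and the wording about confirming absence is a secondary matter.

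*The study is exploratory.* It calls itself so (Sections 1 and 6.2), but it also states a null hypothesis, a sample size for the primary endpoint and a two-sided 5% test. The label does not make a selected comparison a randomised one.

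**Conclusion.** The point holds for efficacy on the text alone. The protocol has one rule on who is analysed, and it selects on a post-randomisation variable that treatment can affect. It would be wrong to call it the only analysis rule, since Section 14.2 sets tests, covariate adjustment and mixed models as well.

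The direction and size of any bias cannot be known from the document. Under one-arm removal of 2 to 4 of 21 and a correlation of 0.3 to 0.5 it is about 0.05 to 0.16 SD, with a type I error of about 5 to 8%. With equal removal it is close to nil. For safety, the conclusion is limited to wording that permits a harmful reading and sits badly with Section 9, which has tests done at discontinuation to evaluate efficacy and safety. The change from 9.5% to 0% shows what that reading would do with assumed counts.

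The rule should be changed before the analysis, because it determines what the primary result means.

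**What to change.** In Section 14.2:

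1. Make the primary efficacy analysis all randomised participants as allocated, using every available week-12 SMI whatever the intake.
2. State a method for missing week-12 SMI, with a sensitivity analysis. Do not substitute discontinuation-visit values. Section 9 promises only the necessary tests and does not name SMI, and such values would alter an endpoint defined at week 12.
3. Keep the set with at least 90% intake as a supportive per-protocol analysis. Define the intake denominator, and replace the open-ended wording with a closed list of criteria fixed before unblinding.
4. State that safety is analysed in everyone who took at least one dose. Replace the aim of confirming absence with the incidence and 95% confidence interval already planned, plus the between-arm difference.

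The cost is small but goes beyond wording. Someone who stops early may have no SMI after baseline, because none is scheduled between screening and week 12, so some missing values will have to be handled. Non-adherence may also dilute the estimated effect slightly.

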Research Protocol

A randomized, placebo-controlled, double-blind, parallel-group study of the effects of nicotinamide mononucleotide on body composition in elderly men

Principal Investigator: [name]

The University of Tokyo Hospital, Department of Diabetes and Metabolism

Address: [name]

[contact]

[contact]

E-mail address: [contact]

Emergency contact: [name]

Planned period of clinical research implementation:

After approval by the Ethics Committee - December 2023

Registration period:

After Ethics Committee approval - December 2019

Clinical Study

A randomized, placebo-controlled, double-blind, parallel-group study of the effect of nicotinamide mononucleotide (NMN) on body composition in elderly men.

Research Protocol

1. Background of the study

A rapidly aging population highlights the need to maintain good physical and mental health in elderly people. Nicotinamide adenine dinucleotide (NAD⁺)-dependent deacetylases sirtuins have received growing attention as longevity genes. Preclinical studies have shown that activation of sirtuins delays the inevitable decline in physiological functions that occur with aging (e.g., muscle strength and immunity to disease).^{1,2,3} It is hypothesized that preventing the age-dependent decline in NAD⁺ levels would prolong the normal physiological function in humans⁴. Given that NAD⁺ is generally not permeable to cell membranes, it is substituted by nicotinamide mononucleotide (NMN) and nicotinamide riboside (NR), two of its precursors, during intervention studies. NMN is a vitamin B3 analog, which is sold and consumed in foods and supplements. At present, there is insufficient clinical evidence supporting the efficacy of NMN ingestion on physiological markers of aging. The proposed clinical trial is a randomized, placebo-controlled, double-blind, parallel-group study of the effects of NMN intake on physiological indicators of aging including body composition changes in healthy elderly men. This study is equivalent to an exploratory study.

[figure not shown]
2. Objectives of the study

The purpose of this study is to determine the efficacy of NMN intake by comparing the body composition of NMN-treated and placebo-treated elderly men.

3. Outline of the food

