4.1 Selection criteria

- 1) Individuals who have received sufficient explanations regarding participation in this study and have given their free written consent with full understanding.
- 2) Males aged 65 years or older at the time of obtaining consent.
- 3) Participants with a body mass index (BMI) between 22 and 28.
- 4) Non-smokers.

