Correlations between blood concentrations of NAD-related metabolites, including NAD, nicotinamide, nicotinic acid (NA), NR, NAR, nicotinic acid mononucleotide (NAMN), nicotinic acid adenine dinucleotide (NAAD), tryptophan, methyl nicotinamide, quinolinic acid, glutathione, adenosine monophosphate (AMP), adenosine diphosphate (ADP), and adenosine triphosphate (ATP), before intake and measured aging markers will be evaluated.

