14.1 Target number of cases and rationale for setting the target

The null hypothesis posits that there is no change in SMI between the NMN intake group and the placebo intake group. Based on existing published evidence⁵, we assumed that the standard deviation for SMI in healthy participants was 0.60 kg/m² and that the expected change in SMI due to food intake was 0.45 kg/m²*. In this case, the sample size that would allow us to reject the above null hypothesis with a 95% confidence interval would be 20 samples for each group (40 samples in total) using calculations based on Cancer Research and Biostatistics. The predicted dropout rate was 5%, and the study was started with 42 participants (21 participants in each group).

*We expect a change of 6–7% based on pre-studies^{6,7}. Given a baseline value for muscle mass loss in the elderly of 6.75 kg/m² for men⁸, the cutoff value for the amount of NMN that could improve muscle mass loss associated with aging was calculated to be $6.75 \text{ kg/m}^2 \times 0.06 = 0.405 \text{ kg/m}^2$ and $6.75 \text{ kg/m}^2 \times 0.07 = 0.4725 \text{ kg/m}^2$. The cutoff value was 0.45 kg/m². Considering that SMI decreases with age, an increase in SMI of 0.45 kg/m² in men aged 70–74 years is equivalent to a rejuvenation of 10–20 years⁹.

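### The NAD-metabolite and aging-marker correlations in 14.2 are unadjusted for age, although the protocol treats NAD⁺ and SMI as falling with age, so a shared age trend can inflate them

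*Protocol*

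**What the plan says.** Section 7 (Evaluation items) lists the blood metabolites and states that correlations between their levels "before intake and measured aging markers will be evaluated". Section 14.2 repeats this for 14 metabolites, saying that the correlation between their blood levels "before oral administration and measured aging markers will be calculated using" one of two named statistics: "Pearson's product rate correlation coefficient (normal distribution) or Spearman's rank correlation coefficient (non-normal distribution". Neither place names age or any other covariate.

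Elsewhere the protocol treats both sides of the best-known pair as age-dependent. Section 1 gives as its hypothesis that "preventing the age-dependent decline in NAD⁺ levels would prolong the normal physiological function in humans". Section 14.1 states: "Considering that SMI decreases with age, an increase in SMI of 0.45 kg/m² in men aged 70–74 years is equivalent to" 10 to 20 years of rejuvenation. Section 4.1 admits "Males aged 65 years or older at the time of obtaining consent", with no upper bound.

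Age is used in two other places. It is a balance criterion for allocation (section 6.10) and a subgroup variable (section 14.2).

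**The concern.** On the protocol's own account, age is a plausible common cause of low NAD⁺ and low SMI. A raw coefficient across participants cannot tell an association between NAD⁺ and muscle at a given age from the fact that older men have less of both. That distinction matters for the hypothesis in section 1, and these correlations are the only specified analysis that relates the metabolites to the markers.

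The provisions already in the protocol do not address this:

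- Balancing age between arms makes the arms comparable. It leaves the age spread across all 42 men as it was.
- The age subgroups are not tied to the correlations.
- The analysis of covariance is for between-group comparison and adjusts for pre-intake values.
- The fallback to other methods applies when the named ones cannot be used, and a Pearson or Spearman coefficient can always be computed here.

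At stake is the reading of a secondary result: an age trend might be reported as support for an NAD-specific link.

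**Working it through.** The protocol gives no figure for these correlations, so there is nothing to reproduce. The check asks how large an age-only association could be.

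**Inputs from the protocol**
- 42 participants (14.1); two-sided 5% level (14.2).
- SMI slope with age (14.1): 0.45 kg/m² corresponds to 10 to 20 years, so 0.45/20 = 0.0225 to 0.45/10 = 0.045 kg/m² per year.
- SD of SMI: 0.60 kg/m² (14.1).

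**Assumptions, not in the protocol**
- SD of age among the enrolled men: 3 to 6 years.
- Correlation of a metabolite with age: 0.2 to 0.5.
- Normal data, with metabolite and marker independent at a given age.

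**Step 1. SMI-age correlation.** In size, r = slope × SD(age) / SD(SMI).

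| Assumed SD of age (years) | Lower slope | Upper slope |
|---|---|---|
| 3 | 0.0225 × 3 / 0.60 = 0.11 | 0.045 × 3 / 0.60 = 0.23 |
| 4 | 0.15 | 0.30 |
| 5 | 0.19 | 0.38 |
| 6 | 0.23 | 0.45 |

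The range is about 0.11 to 0.45.

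**Step 2. Induced correlation.** If age is the only link, r(metabolite, marker) = r(metabolite, age) × r(marker, age). With n = 42, a raw coefficient is significant when |r| exceeds t / √(n − 2 + t²), with t the 97.5% point on 40 degrees of freedom. That threshold is 0.304.

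**Step 3. How often the raw coefficient is significant.** Simulation of at least 20,000 trials per row, n = 42, Pearson coefficients:

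| SMI-age r | Metabolite-age r | Induced r | Raw significant | Age-partial significant |
|---|---|---|---|---|
| 0.11 | 0.2 | 0.02 | 5% | 5% |
| 0.2 | 0.2 | 0.04 | 6% | 5% |
| 0.2 | 0.5 | 0.10 | 10% | 5% |
| 0.3 | 0.5 | 0.15 | 16% | 5% |
| 0.38 | 0.5 | 0.19 | 23% | 5% |
| 0.45 | 0.2 | 0.09 | 9% | 5% |
| 0.45 | 0.5 | 0.225 | 30% | 5% |

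Over an SMI-age correlation of 0.2 to 0.45, the raw test is significant in about 6% to 30% of trials. At the lowest SMI-age correlation it stays close to 5%. The partial coefficient holds 5% in every row.

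**The case against.** The strongest objection is that these rates are not type I errors of the test as written. If age links the two variables, their population correlation is not zero, and rejecting zero is correct. The protocol asks only whether metabolites correlate with aging markers, states no age-independent estimand and draws no causal conclusion. This stands. The raw coefficient is a valid description, and the 5% benchmark applies only when it is read as a link beyond age.

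The premise is also narrow. The protocol mentions an age decline for NAD⁺, within a hypothesis and without saying that it refers to blood levels or to men over 65, and for SMI. It says nothing of the kind about the other 13 metabolites or most markers. It also leaves open whether the markers are baseline values or changes. For changes, a cross-sectional age decline would not establish confounding. This stands too, and it limits how far the point extends beyond NAD⁺ and SMI.

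A further objection is that covariates for an exploratory correlation can be left to a statistical analysis plan that is not shown. This carries less weight, because 14.2 does not leave the method open: it names a bivariate coefficient. Section 14.2 also promises an analysis of the effect of endpoints on parameters, but too vaguely to count as an age adjustment.

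A reader might infer that age alone will produce significant associations, in a third or two thirds of trials. Rates of about 36% and 66% need age correlations of 0.5 and 0.6 on both sides. The slope in 14.1 gives at most about 0.45 for SMI, even with an age SD of 6 years, and no metabolite-age correlation is given. The documents do not support that reading.

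**Conclusion.** The point holds as a minor one. Section 14.2 fixes unadjusted correlations between variables of which at least one pair, NAD⁺ and SMI, is treated by the protocol as falling with age. A shared age trend can create or inflate such a correlation. The inflation is negligible if both age correlations are about 0.2 or less. It reaches roughly 30% significant results, against 5% for the age-partial coefficient, at the upper end of the range examined (0.45 for SMI and 0.5 for the metabolite).

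These figures rest on an assumed age SD of 3 to 6 years, an assumed metabolite-age correlation, and the slope and SD in 14.1 applying to the men enrolled. The analysis is secondary in a study that calls itself exploratory. The randomised comparison of NMN with placebo is not affected.

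**What to change.** In section 14.2, with a matching phrase in section 7:

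- Report beside each raw coefficient the partial correlation adjusted for age, with a 95% confidence interval. Choose Pearson or Spearman by the rule already in 14.2.
- State that the raw coefficient is descriptive, and that any statement of a link independent of age rests on the adjusted one.

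The existing choice between Pearson and Spearman need not change. BMI should not be added as a routine covariate: SMI and BMI share height² as denominator, and weight at a given BMI is little more than height, so that adjustment would change the question.

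The cost is about one sentence and one degree of freedom per coefficient. Date of birth is already recorded at screening (section 8), so no new data are needed.
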